9.4.1 Efficacy analyses

Table 6 - Efficacy analyses

Endpoint	Statistical Analysis Methods
Primary	
Coprimary endpoint in the primary population: Percent change in CSF GM2 biomarker from baseline to Week 104
 
Percent change in CSF GM2 biomarker from baseline to Week 104 will be analyzed using an ANCOVA including the fixed effect of treatment (venglustat versus placebo) and the continuous fixed covariate of baseline value.
 
In case the results from the ANCOVA may be severely impacted by the presence of outliers (participants with extremely low or high percent change in CSF GM2), the ANCOVA will be replaced by a robust ANCOVA, using Huber's M estimation. The robust ANCOVA will also include the fixed effect of treatment (venglustat vs. placebo) and the continuous fixed covariate of baseline value.
 
The exact criterion to determine whether the robust ANCOVA should be used will be described in the Statistical Analysis Plan (SAP).
 
Annualized rate of change in 9-HPT from baseline to Week 104
 
Annualized rate of change in 9-HPT will be compared between venglustat and placebo using a linear mixed-effect model.
 
The model will assume linear change over time in 9-HPT (after log transformation). The logarithm transformation was selected due to anticipated non-normal distribution of the 9-HPT. Analysis of natural history data showed that logarithm transformation improved the normality of the distribution and reduced the impact of outliers. A logarithm transformation will allow interpretation in terms of relative increase in time to complete the 9-HPT (annual % increase per year).
 
The model will include separate slopes for the venglustat and placebo arms. Actual time relative to randomization of all planned assessments at Week 12, Week 26, Week 52, Week 78, and Week 104 will be taken into account in the model. In addition, the model will include a random intercept and slope in order to account for the between participants variability. A residual variance will account for the within-participant variability.
 
The linear mixed-effect model will be estimated in a Frequentist framework.
 
If the results from the linear mixed-effect model are severely impacted by the presence of data outliers (participants with extremely low or extremely high slope of log-transformed 9-HPT), the linear mixed-effect model will be replaced by the robust ANCOVA on individual slopes.

[Redacted content]

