2.1.1 Estimands

Primary estimand defined for main endpoints are summarized in below [Table 4](#). More details are provided in [Section 3](#).

Table 4 - Summary of primary estimand for main endpoints

Endpoint Category (estimand)	Estimands			
	Endpoint	Population	Intercurrent event(s) handling strategy	Population-level summary (Analysis and missing data handling)
Primary population				
Primary objective: To assess the efficacy of daily oral dosing of venglustat when administered over a 104-week period.				
Primary endpoint (treatment policy)	Annualized rate of change in the 9-HPT from baseline to Week 104	Primary efficacy population	Regardless of adherence to study intervention	Difference in mean slope of the 9-HPT from baseline to Week 104, estimated from a linear mixed effect model after log transformation. In case of outliers, the linear mixed effect model will be replaced by a robust ANCOVA on individual slopes. No imputation of missing data due to small sample size.
Primary objective: To assess the PD of daily oral dosing of venglustat when administered over a 104-week period.				
Primary endpoint (treatment policy)	Percent change in CSF GM2 biomarker from baseline to Week 104	Primary pharmacodynamic population	Regardless of adherence to study intervention	Difference in mean percent change in CSF GM2 biomarker from baseline to Week 104, estimated from ANCOVA. In case of outliers, the ANCOVA will be replaced by a robust ANCOVA. No imputation of missing data due to small sample size.
Secondary objectives: To assess the PD of daily oral dosing of venglustat when administered over a 104-week period				
Secondary endpoint (treatment policy)	Absolute change in CSF GM2 biomarker from baseline to Week 104	Primary pharmacodynamic population	Regardless of adherence to study intervention	Difference in mean absolute change in CSF GM2 biomarker from baseline to Week 104, estimated from ANCOVA. In case of outliers, the ANCOVA will be replaced by a robust ANCOVA. No imputation of missing data due to small sample size.
Secondary objectives: To assess the effect of venglustat on selected performance test and scale over a 104-week period.				

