3 STATISTICAL ANALYSES

3.1 GENERAL CONSIDERATIONS

Statistical significance for comparison between venglustat and placebo will be assessed at the Type I error rate of 0.05 one sided. Although a typical criterion for concluding that a trial is positive is a p-value of <0.05 two-sided, a higher Type I error rate of 0.05 one-sided was selected due to the rarity of late-onset GM2 gangliosidosis, the seriousness of this disease and lack of available therapy, as per Food and Drug Administration (FDA) draft guidance (1).

In general, continuous data will be summarized using the number of observations available, mean, standard deviation (SD), median, [Q1, Q3] minimum, and maximum. Categorical and ordinal data will be summarized using the count and percentage of participants.

The baseline value is defined as the last available value before or equal to the first dose of investigational medicinal product (IMP) date in the primary analysis period. For participants randomized but not exposed, the baseline value is defined as the last available value before or equal to the date of randomization.

Unless otherwise specified, analyses will be performed by intervention group (and overall for baseline and demographics characteristics).

The two analysis periods described below are defined:

- The **primary analysis period** is defined as the period starting at the date of signed informed consent, and ending at the end of Week 104 visit, or the day before the first IMP OLE administration (whichever comes last). For participants not exposed to IMP in the OLE, the primary analysis period ends at the date of end of study.
- The **OLE period** (only for participants exposed to IMP in the OLE) is defined as the period starting the day after the end of primary analysis period, until the end of the study.

Within each analysis period, the following observation periods are defined:

During the **primary analysis period** (as defined above), the following observation periods are defined:

- The **pre-treatment period** is defined as the time from the signed informed consent date up to the first IMP administration.
- The **treatment-emergent (TE) period** is defined as the time from the first IMP administration to the last administration of IMP during the primary analysis period +6 weeks (including any temporary treatment discontinuation period, if any) or the end of the primary analysis period (whichever comes first).

The TE period includes the following 2 periods:

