The second co-primary endpoint in the primary population is the annualized rate of change in 9-HPT from baseline to Week 104.

3.2.2.2 *Main analytical approach*

[figure not shown]
The primary analysis will include all data collected in patients from the primary population, regardless of whether or not participants completed the treatment period. Patients who prematurely and permanently discontinue study medication will be requested to continue to be assessed after treatment discontinuation, up to the Week 104 visit. Data collected after treatment discontinuation will be included in the primary analysis. All efforts will be made to minimize the amount of missing data.

The 9-HPT will be derived from the two trials for each hand (see [Section 5.5.1](#) for derivation of the 9-HPT).

Annualized rate of change in 9-HPT will be compared between venglustat and placebo using a linear mixed-effect model.

The model will assume linear change over time in 9-HPT after log transformation. The logarithm transformation was selected due to anticipated non-normal distribution of the 9-HPT. Analysis of natural history data showed that logarithm transformation improved the normality of the distribution and reduced the impact of outliers (see [Figure 1](#)). A logarithm transformation will allow interpretation in terms of relative increase in time to complete the 9-HPT (annual % increase per year).

Figure 1 - Distribution and QQ-plot of Studentized residuals from the linear mixed-effect model on natural history data - With or without log transformation

The model will include separate slopes for the venglustat and placebo arm. In addition, the model will include random intercept and slope in order to account for the between subjects variability. A residual variance will account for the within-subject variability.

The linear mixed-effect model is based on the following equation:

$$y_{ijk} = \alpha_j + \beta_j t_{ijk} + u_{1ij} + u_{2ij} t_{ijk} + \varepsilon_{ijk}$$

Where:

- y_{ijk} is the log-transformed 9-HPT of subject i from group j at the k^{th} assessment.
- t_{ijk} is the time (in years) from randomization of the k^{th} assessment of 9-HPT.
- α_j is the fixed intercept of group j .
- β_j is the fixed slope of group j .
- u_{1ij} and u_{2ij} are the random intercept and random slope of subject i from group j .
- ε_{ijk} is the residual error.

The linear mixed-effect model makes the following assumptions:

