3.2.2.4.2 While-on-treatment analysis

A secondary analysis will target a while-on-treatment estimand.

In this sensitivity analysis, the linear mixed-effect model described in [Section 3.2.2.2](#) will be repeated, including only 9-HPT collected during the primary analysis period, up to the last IMP administration +30 days.

In case of presence of outlier, the linear mixed-effect model will be replaced by the robust ANCOVA on individual slopes, described in [Section 3.2.2.3.1](#). The exact criterion to detect outliers is presented in [Section 5.6.1.2](#).

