3.8.2 Final analysis

The final analysis will be conducted in two steps:

First step: Primary analysis period:

- The analysis of the primary analysis period of the study will be conducted when all participants have completed the primary analysis period of the study. It will consist in the final analysis of the primary, secondary, and exploratory endpoints at 104 weeks. The analysis of the primary analysis period will be conducted when all participants have completed the Week 104 visit or have prematurely discontinued the study.

- The cut-off date for the first step analysis will be the date of the last visit of the last participant during the primary analysis period.
- The analysis of the primary analysis period of the study will include all data collected up to the Week 104 visit. Any data collected during the open-label extension treatment period will not be included in this first step analysis.
- In order to further document safety for regulatory purpose, an overview of adverse events occurring during the open-label extension, up to the cut-off date of the primary analysis period will be provided.

Second step: analysis of the open-label extension treatment period:

- The analysis of the open-label extension treatment period of the study will be conducted when all participants have completed the Week 208 visit and safety follow up visit or have prematurely discontinued the study.

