5.6.3.3 SAS code used to conduct the simulations

```

/*****************************;
/* STEP 1 : Definition of simulation parameters */;
/*****************************;

* Number of simulations;
%let Nsim = 10;

* Total number of patients on venglustat and placebo;
%let NpatV = 38;
%let NpatP = 19;

* List of time-points (in years) ;
%let listtime = 0,0.25,0.50,1,1.50,2.0;

* Seed of simulations ;
%let seed = 15299;

* Drop out rate (at time tdrop) ;
%let rdrop = 0.1;

```

```
%let tdrop = 2;

* Mean and SD of intercept ;
%let mI = 3.5551;
%let sdI = 0.4841;

* Mean slopes on Placebo ;
%let mS_P = 0.0273;

* SD of random slopes (between subject SD) ;
%let sdS = 0.0192;

* SD of residual error (within subject SD) ;
%let sdR = 0.0791;

* Scenarios for the difference in slope (list separated by commas);
%let diff = -0.0374,0;

* Number of scenarios for extreme values;
%let Nsce = 10;

* Base scenario (protocol assumption, no extreme patient ;
%let pE1 = 0;
%let mE1 = 0;
%let sE1 = 1;

* Scenario with 1% extreme patients having mean slope = 0.4;
%let pE2 = 0.01;
%let mE2 = 0.4;
%let sE2 = 0.0192;

* Scenario with 1% extreme patients having mean slope = 0.7;
%let pE3 = 0.01;
%let mE3 = 0.7;
%let sE3 = 0.0192;

* Scenario with 1% extreme patients having mean slope = 0.9;
%let pE4 = 0.01;
%let mE4 = 0.9;
%let sE4 = 0.0192;

* Scenario with 2% extreme patients having mean slope = 0.4;
%let pE5 = 0.02;
%let mE5 = 0.4;
%let sE5 = 0.0192;

* Scenario with 2% extreme patients having mean slope = 0.7;
%let pE6 = 0.02;
%let mE6 = 0.7;
%let sE6 = 0.0192;

* Scenario with 2% patients having mean slope = 0.9;
%let pE7 = 0.02;
%let mE7 = 0.9;
%let sE7 = 0.0192;
```

```
* Scenario with 5% extreme patients having mean slope = 0.4;
%let pE8 = 0.05;
%let mE8 = 0.4;
%let sE8 = 0.0192;

* Scenario with 5% extreme patients having mean slope = 0.7;
%let pE9 = 0.05;
%let mE9 = 0.7;
%let sE9 = 0.0192;

* Scenario with 5% extreme patients having mean slope = 0.9;
%let pE10 = 0.05;
%let mE10 = 0.9;
%let sE10 = 0.0192;
/*********************************************************************
/* STEP 2 : Simulation of clinical trial data under different scenarios */
/********************************************************************

/* Simulation of clinical trial data */
data SimData(keep=diff sce pE mE sE sim subject group base time log9hpt);
length diff sce pE mE sE sim subject group base time log9hpt 8;

retain seed &seed;

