* Assess different scenarios for difference and extreme patients ;
do diff = &diff;
do sce = 1 to &Nsce;

  * Get proportion of extreme patients in the current scenario ;
  pE = input(symget("pE"||compress(put(sce,best.))),best.);

  * Get mean slope of placebo for extreme patients in the current scenario ;
  mE = input(symget("mE"||compress(put(sce,best.))),best.);

  * Get SD of slope for extreme patients in the current scenario ;
  sE = input(symget("sE"||compress(put(sce,best.))),best.);

  * Generate simulated clinical trial data for the current scenario;
  do sim=1 to &Nsim;
  do subject = 1 to &NpatV+&NpatP;

    * Assign patients to venglustat or placebo arm ;
    if subject <= &NpatV then group = 1;
    else group = 0;

    * Randomly determine if patient is normal or extreme, and determine mean
    and SD of slope of this patient ;
    call ranuni(seed,u);
    if u > pE then do; mS = &ms_P + group*diff; sdS = &sdS; end;
    if u < pE then do; mS = mE + group*diff; sdS = sE; end;

    * Simulate time to dropout (assuming exponential time to drop-out and
    rate at time &tdrop is &rdrop) ;
    call ranuni(seed,x);
    tdrop = log(x)*&tdrop/log(1-&rdrop);

  end;
  end;

  * Output simulated data ;
  output;
end;
end;
```

```
* Generate a random intercept for the current patient ;
call rannor(seed,int);
int = &mI + int*&sdi;

* Generate a random slope for the current patient ;
call rannor(seed,slope);
slope = mS + slope*sds;

* Create observations at each time-point ;
do time=&listtime;

* Generate a residual error for the current observation ;
call rannor(seed,e);
e = &sdR*e;

* Generate a log(9-HPT) measurement at the given time-point ;
log9hpt = int + slope*time + e;

* Baseline value;
if time = 0 then base = log9hpt;

* Keep only observations before patient drops out ;
if time<tdrop then output;
end;

end;
end;

end;
end;
run;

/* Calculate number observations per subject */
proc means data=SimData nopolish nway;
class diff sce pE mE sE sim subject;
var log9hpt;
output out=nobs(keep=diff sce pE mE sE sim subject nobs) n=nobs;
run;
data Simdata;
merge simdata nobs;
by diff sce pE mE sE sim subject;
run;

/* Calculate individual slopes (for patients with at least 2 observations) */
ods listing close;
options nonotes;
proc mixed data=SimData;
where nobs >= 2;
by diff sce pE mE sE sim subject group base;
model log9hpt = time / s;
ods output solutionF=indSlope(where=(effect="time"))
rename=(estimate=slope));
run;
ods listing;
options notes;
```

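### Does starting the primary analysis period at consent let the screening 9-HPT into the slope model?

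*SAP*

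**What the plan says.** Protocol 1.3 schedules the 9-HPT at screening, up to 60 days before Day 1, and again at Day 1.

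Three places in the SAP could be read as admitting the screening test:

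- Section 3.1 says of the primary analysis period that it "is defined as the period starting at the date of signed informed consent, and ending at the end of Week 104 visit", extended to the eve of the first open-label extension (OLE) dose if that is later. Section 3.2.2.4.2 uses this period for the while-on-treatment analysis, "including only 9-HPT collected during the primary analysis period, up to the last IMP administration +30 days".
- Section 3.8.2: the first-step analysis "will include all data collected up to the Week 104 visit".
- Section 3.2.2.2: the time variable "is the time (in years) from randomization of the" assessment concerned, with no lower limit given.

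Other places point to a single pre-dose record:

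- SAP 2.1.1, Table 4 gives the endpoint as "Annualized rate of change in the 9-HPT from baseline to Week 104".
- SAP 3.1 defines baseline as one value, the last available on or before the date of first dose.
- Protocol 1.3 designates Week 1/Day 1 as the baseline visit.
- The simulation code in SAP 5.6.3.3 sets "let listtime = 0,0.25,0.50,1,1.50,2.0" and then "if time = 0 then base = log9hpt".

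Protocol 9.4.1, Table 6 adds that "all planned assessments at Week 12, Week 26, Week 52, Week 78, and Week 104 will be taken into account in the model".

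**The concern.** The slope model uses actual assessment times, so a screening test could be fitted at a negative time without any error message. The period named in the while-on-treatment analysis begins at consent and therefore contains that test. The protocol's visit list does not settle the matter, because it starts at Week 12 and omits even Day 1.

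The 9-HPT is the limiting co-primary endpoint, with about 80% power against more than 99% for CSF GM2. If the choice were open at unblinding, two defensible data sets would exist. The sizes below assume a screening gap of 30 or 60 days and a correlation of 0 to 0.9 between the two pre-dose errors.

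- The two readings disagree on significance in 6 to 10% of trials at the planned difference, and in 2.3 to 3.8% under no effect.
- Taking the more favourable result afterwards would raise Type I error from 5.0% to 6.2-6.9%.
- A simulation of the SAP's switching rule (30 days, correlation 0.5, 1,400 trials) gave 4.4% disagreement under no effect, and 8.3% of trials with either reading significant. With the single baseline record the rate was 5.4%.

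The while-on-treatment model might also differ from the main model by more than its estimand.

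**Working it through.** **1. What each passage does.**

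- *Section 3.2.2.4.2* repeats the Section 3.2.2.2 model on a subset of records. A restriction cannot add a record that the main model lacks. Its working limits are the end of the primary analysis period and the 30 days after last dose. The first limit matters because placebo participants receive venglustat in the OLE, where the 9-HPT continues at Weeks 156 and 208.
- *Section 3.8.2* sets an upper cut-off. Its next sentence excludes OLE data.
- *Section 3.2.2.2* calls for all collected data in order to keep assessments made after treatment discontinuation, as the sentences around it show.
- *Baseline.* A screening test taken before a Day 1 test lies outside an interval that starts at baseline. The emergency rules in Protocol 10.11 agree: other screening results may stand in at Day 1, but the 9-HPT must be repeated.

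**2. The plan's own power figure.** Inputs from the code in SAP 5.6.3.3: slope SD 0.0192, residual SD 0.0791, difference -0.0374, 38 versus 19 participants, 10% dropout by 2 years. SAP 3.1 gives one-sided 0.05.

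Completers at 0, 0.25, 0.5, 1, 1.5 and 2 years:

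- Mean time = 5.25/6 = 0.875. Centred sum of squares = 7.5625 - 6 × 0.875² = 2.96875.
- Variance of one participant's slope = 0.0192² + 0.0791²/2.96875 = 0.000369 + 0.002108 = 0.002476, so SD = 0.0498.
- SE of the difference = 0.0498 × √(1/38 + 1/19) = 0.0498 × 0.2810 = 0.01398.

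Allowing for dropout, the SE is 0.01458. Normal-approximation power = Φ(0.0374/0.01458 - 1.645) = Φ(0.920) = 82.1%. With a t distribution on 55 df it is 81.3%, and 2,000 simulated REML fits give 79.95%. The stated figure of about 80% therefore belongs to the single-baseline analysis.

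**3. The other possible record sets, same inputs.**

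| Pre-dose records | SE | Power (normal) | Power (t, 55 df) |
|---|---|---|---|
| One, at time 0 | 0.01458 | 82.1% | 81.3% |
| None (Weeks 12-104 only) | 0.01717 | 70.3% | 69.4% |
| Time 0 plus screening at day -30, independent errors | 0.01321 | 88.2% | 87.5% |

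The second row shows that the protocol's list cannot be the full set of records. It names the post-baseline visits, and the baseline value enters through the endpoint definition. The third row assumes independent errors and a screening value on the same line as later values. With correlated errors and a common slope before randomization, power at either gap is 80.3 to 87.2%. Power alone therefore does not rule out the screening record; the code does, because it contains no such record.

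**4. Effect on the treatment contrast.** Suppose screening times are 5% slower for practice reasons (assumed). At a 30-day gap, each arm's slope moves by -0.2185 × ln 1.05 = -0.2185 × 0.0488 = -0.0107 per year. Both arms move alike: in 600 simulated trials the difference stayed at -0.0371. If the slope before randomization is common to both arms, including screening shrinks the difference by 0.0007 (30 days) to 0.0015 (60 days). That is 2 to 4% of 0.0374.

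**The case for a change.** The best case for a change is that it costs one sentence. No visible text says that the screening test is excluded. The visit windows in SAP Table 13 govern by-visit summaries, so their lack of a pre-dose window proves little for a model in actual time. The 25-foot walk and FARS-neuro analyses inherit the same silence. The supportive Bayesian analysis is more exposed than the frequentist one, because only the placebo slope carries an informative prior. With practice shifts of 2.5%, 5% and 10%, its false-positive rate would go from 2.6% to 4.8%, 8.2% and 19.8%.

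The missing sentence is real. The rest weakens on inspection. The Type I error figures require the reading to be chosen after results are seen. The Bayesian figures require that choice as well as an assumed shift falling wholly between screening and Day 1. The documents give no error correlation or practice effect, so none of these sizes describes the plan as written.

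An edit also carries a risk. Replacing the period in Section 3.2.2.4.2 with a phrase such as from baseline would remove that section's own barrier against OLE data. Only Section 3.8.2 would then keep those records out, and only in the first-step analysis.

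**Conclusion.** No change follows. This is missing detail that the plan's other statements fill in one direction: one baseline value, normally Day 1, plus assessments up to Week 104. If Day 1 is missing, the baseline definition in SAP 3.1 already makes the screening value the baseline. That analysis matches the estimand and the code, and its power reproduces at 79.95% (simulated) to 81.3% (analytic, t) against the stated 80% or so. The consent-start wording selects 9-HPT records in one supportive analysis only, as a restriction.

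The programming specification for the slope data set can record the rule without a SAP amendment. The conclusion rests on the visible text. SAP 3.2.2.3.1 and the simulation method in 5.6.3.1 are not shown in the public copy, so nothing is inferred from them.
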